## 2 PROTOCOL SYNOPSIS

**Title** A Phase 1/2 Study of VX-121 in Healthy Subjects and in Subjects With Cystic Fibrosis

**Clinical Phase and Clinical Study Type** Phase 1/2 safety, tolerability, pharmacokinetics (PK), pharmacodynamics (PD), and efficacy

**Objectives** Primary Objectives

**Part A:** To evaluate the safety and tolerability of single ascending doses of VX-121 in healthy subjects

**Part B:** To evaluate the safety and tolerability of multiple ascending doses of VX-121 for 10 days in healthy subjects

**Part C:** To evaluate the safety and tolerability of multiple ascending doses of VX-121 administered in triple combination (TC) with tezacaftor (TEZ)/ivacaftor (IVA) for 14 days in healthy subjects

**Part D:** To evaluate the safety and tolerability of VX-121 in TC with TEZ/IVA in subjects with cystic fibrosis (CF)

Secondary Objectives

**Part A**

- To evaluate the PK of VX-121 after administration of single ascending doses of VX-121 in healthy subjects
- To evaluate the relative bioavailability (BA) of a tablet formulation of VX-121 relative to suspension in healthy subjects
- To evaluate the effect of milk on the PK of VX-121 after administration of suspension and tablet formulations

**Part B**

To evaluate the PK of VX-121 after administration of multiple ascending doses of VX-121 for 10 days in healthy subjects

**Part C**

- To evaluate the PK of VX-121 after administration of multiple ascending doses of VX-121 in TC with TEZ/IVA for 14 days in healthy subjects
- To evaluate the PK of TEZ, IVA, and their respective metabolites when administered in TC with VX-121 for 14 days in healthy subjects

**Part D**

- To evaluate the PK of VX-121 when administered in TC with TEZ/IVA in subjects with CF
- To evaluate the PK of TEZ, IVA, and their respective metabolites when administered in TC with VX-121 in subjects with CF
- To evaluate the PD effect of VX-121 in TC with TEZ/IVA in subjects with CF
- To evaluate the efficacy of VX-121 in TC with TEZ/IVA in subjects with CF

**Endpoints** Primary Endpoint

**Parts A, B, C, and D:** Safety and tolerability, based on the assessment of adverse events (AEs), laboratory test results, standard 12-lead ECGs, vital signs, and spirometry (Part D only)

**Secondary Endpoints**

- **Parts A, B, C, and D:** PK parameter estimates of VX-121 derived from plasma concentration-time data
- **Parts C and D:** PK parameter estimates for TEZ and metabolites (M1-TEZ and M2-TEZ) and IVA and metabolites (M1-IVA and M6-IVA) derived from plasma concentration-time data
- **Part D:** Sweat chloride levels as a biomarker of PD effects
- **Part D:** Spirometry as preliminary evidence of efficacy

**Number of Subjects** Approximately 132 subjects: 56 in Part A, 48 in Part B, 16 in Part C, and 12 in Part D

**Study Population** **Parts A, B, and C:** Healthy male subjects and female subjects of non-childbearing potential between the ages of 18 and 55 years, inclusive  
**Part D:** Male subjects and female subjects of non-childbearing potential with CF, heterozygous for *F508del* and a minimal *CFTR* function mutation that is not responsive to TEZ, IVA, or TEZ/IVA (F/MF genotypes), ages 18 and older

**Investigational Drug** **Parts A and B**  
Active substance: VX-121  
Activity: CFTR corrector  
Strength and route of administration:  
Suspension: Drug substance will be reconstituted at various concentrations for oral administration  
Tablet: 5-mg tablet for oral administration

**Parts C and D**

Active substance: VX-121  
Activity: CFTR corrector  
Strength and route of administration:  
Suspension: Drug substance will be reconstituted at various concentrations for oral administration  
Tablet: 5-mg tablet for oral administration

Active substance: TEZ (VX-661) and IVA (VX-770)  
Activity: CFTR corrector and potentiator ( $\text{Cl}^-$  secretion)  
Strength and route of administration: 100-mg TEZ/150-mg IVA, film-coated fixed-dose combination (FDC) tablet for oral administration

Active substance: IVA (VX-770)  
Activity: CFTR potentiator  
Strength and route of administration: 150-mg film-coated tablet for oral administration

**Study Duration** Excluding the Screening Period, the study duration for each subject is 9 to 12 days for Cohorts A1, A2, A4, A5, and A6, 18 to 20 days for Cohort A3, 26 to 28 days for Cohort A9, 18 to 21 days for Part B, 22 to 25 days for Part C, and

approximately 7 to 9 weeks for Part D.

**Study Design**

This is a 4-part, randomized, double-blind, placebo-controlled, single- and multiple-dose, first-in-human and first-in-patient dose escalation study of VX-121 that includes an evaluation of relative BA and the effect of milk on VX-121 exposure.

**Parts A, B, and C (Healthy Subjects)**

Approximately 7 cohorts are planned for Part A (A1 through A6 and A9), approximately 6 cohorts are planned for Part B, and approximately 2 cohorts are planned for Part C. Up to 2 additional cohorts each in Parts A, B, and C may be enrolled based on data from previous cohorts.

Approximately 8 subjects in each cohort (except Cohort A9) will be randomized 3:1 to receive VX-121 (or VX-121 in TC with TEZ/IVA in Part C) or placebo as a suspension, under fed conditions. All subjects in Cohort A3 will also receive an open-label dose of VX-121 to evaluate the effect of milk on a suspension formulation. Cohort A9 will enroll approximately 8 subjects who will receive open-label VX-121 to evaluate the BA of a tablet relative to suspension formulation and the effect of milk on the tablet formulation. The tablet formulation may then be used instead of the suspension in any remaining cohorts of the study if supported by preliminary PK data from Cohort A9. The existing restrictions on dairy consumption may be removed pending the results from Cohorts A3 and/or A9.

The decision to initiate successive cohorts and dose selection will be based on safety and tolerability data from preceding dose group(s) and available PK data from a minimum of 6 subjects (to ensure 4 subjects receiving active drug) in the preceding cohort.

**Part A** includes Cohorts A1 through A6, which are single-dose escalation cohorts. Up to 2 additional cohorts (Cohorts A7 and A8) may be enrolled based on data from previous cohorts. Cohort A9 is a single-dose cohort evaluating relative BA. Cohorts A1 Through A6 (up to A8): VX-121 or placebo will be administered, on the morning of Day 1. The starting dose (Cohort A1) will be 10 mg. [REDACTED]

[REDACTED] Dosing will be staggered in Cohort A1 so that 2 subjects are dosed (1 with VX-121 and 1 with placebo) at least 24 hours before the remaining 6 subjects. Staggering at higher doses may be conducted if deemed necessary based on review of emerging safety data. The planned doses for Cohorts A1 through A6 are 10 mg, 20 mg, 5 mg, 40 mg, 60 mg, and up to 90 mg. Doses may be modified based on emerging data. If conducted, the dose(s) in Cohorts A7 or A8 may be a replicate of a dose evaluated in Cohorts A1 through A6 or may be increased above 90 mg, pending emerging safety, tolerability, and PK data from Cohorts A1 through A6.

Cohort A3: In addition to randomized study drug administration described above, after a washout of at least 8 days all subjects will receive an additional 5 mg single dose of open-label VX-121 suspension with milk.

Cohort A9 has an open-label, single sequence design in which subjects will receive a single dose of VX-121 on 3 dosing occasions with at least an 8-day washout between dosing occasions. VX-121 doses include a single oral dose of suspension, a single oral dose of tablet, and a single oral dose of tablet with milk (the planned dose is 10 mg for both formulations, but it will not exceed the highest dose that was safe and well tolerated in a previous Part A cohort).

**Part B** is a 6-cohort, multiple-dose escalation component (Cohorts B1 through B6). Up to 2 additional cohorts (Cohorts B7 and B8) may be conducted. Multiple oral

doses of VX-121 or placebo will be administered for 10 days once daily (qd).

The planned doses for Cohorts B1 through B4 are 10 mg qd, 20 mg qd, 40 mg qd, and 60 mg qd. Doses may be modified based on emerging data. The doses for Cohorts B5 and B6 are to be determined (TBD) based on emerging data.

Part B may be initiated while Part A is ongoing after review of safety, tolerability, and PK data. The total daily dose in the first Part B cohort (Cohort B1) will be at least 1 dose level below the highest Part A dose for which safety and tolerability results are available and supportive.

**Part C** is a 2-cohort, multiple-dose escalation of VX-121 administered in TC with TEZ/IVA for 14 days (Cohorts C1 and C2). Up to 2 additional cohorts (Cohorts C3 and C4) may be conducted.

The planned doses for Cohorts C1 and C2 are 10 mg qd and 20 mg qd. Doses may be modified based on emerging data. The dosage of TEZ/IVA will be TEZ 100 mg qd/IVA 150 mg q12h, which will be administered as TEZ 100 mg/IVA 150 mg FDC in the morning and IVA 150 mg in the evening.

Part C may be initiated while Parts A and B are ongoing after review of safety, tolerability, and PK data.

The total daily dose in the first Part C cohort (Cohort C1) will be at least 1 dose level below the highest total daily Part B dose for which safety and tolerability results are available and supportive. Dosing will be staggered in Cohort C1, with 2 of the 8 subjects receiving study drug (1 subject receiving VX-121 in TC with TEZ/IVA and 1 subject receiving triple placebo) at least 24 hours before the remaining 6 subjects. Staggering at higher doses may be conducted if deemed necessary based on review of emerging safety data.

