g Blood samples for PK assessments will be collected on Days 1, 9, and 17 before dosing (0 hours), and at 1, 1.5, 2, 3, 4, 5, 6, 8, 12, 24 (Days 2, 10, 18), 36 (Days 2, 10, 18), 48 (Days 3, 11, 19), 72 (Days 4, 12, 20), 96 (Days 5, 13, 21), 120 (Days 6, 14, 22), 144 (Days 7, 15, 23), and 168 (Days 8, 16, 24) hours after dosing. Acceptable PK sampling windows are provided in [Table 11-1](#). At the Safety Follow-up Visit, a single blood sample for PK analysis will be collected.

h Study drug will be administered as a suspension in the fed state on the Day 1 Visit, as a tablet in the fed state on the Day 9 Visit, and as a tablet in the fed state and with milk on the Day 17 Visit ([Section 9.6.1](#)).

i All medications taken from 28 days before the first dose of study drug through the end of the study will be recorded.

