#### 9.1.1 Parts A, B, and C (Healthy Subjects)

A schematic of the study design for Parts A, B, and C is shown in [Table 9-1](#). Up to 2 additional cohorts each in Parts A (Cohorts A7 and A8), B, and C may be enrolled based on data from previous cohorts; these cohorts will follow the corresponding schedule of assessments.

There is no prespecified ratio of males to females, but reasonable effort will be made to enroll females of non-childbearing potential in all dosing cohorts. Subjects will be allowed to participate in up to 2 cohorts (subjects may enroll in 2 cohorts in Part A or 1 cohort in Part A and 1 cohort in either Part B or Part C; see [Section 9.1.1.1](#)).

The decision to initiate successive cohorts and dose selection will be based on safety and tolerability data from preceding dose group(s) and available PK data from all subjects in the preceding cohort (minimum of 6 subjects to ensure 4 subjects receiving active drug). Refer to [Section 9.7.1](#) for dose escalation criteria and [Section 9.8.1](#) for stopping rules.

Subjects will receive VX-121 as a suspension, under fed conditions. The tablet formulation may be used instead of the suspension in any remaining cohorts of the study if supported by preliminary PK data from Cohort A9. The existing restrictions on dairy consumption ([Section 9.4.1](#)) may be removed pending the results from Cohorts A3 and/or A9.

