#### Cohort A9

[figure not shown]
Cohort A9 will not be initiated until all documentation required to support administration of the VX-121 tablet has been submitted to and approved by the competent authority (IRB/IEC, as applicable).

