### **9.3 Rationale for Study Design and Study Drug Regimens**

#### **9.3.1 Study Design**

#### **Parts A, B, and C**

Parts A (except Cohort A9) and B have a dose-escalation design, with each subject participating in only 1 cohort (unless at least 21 days has elapsed before participation in another cohort), to avoid PK and/or PD carryover effects.

Part C will evaluate the safety, tolerability, and PK of VX-121 administered in TC with TEZ/IVA because VX-121 is being developed for use in this TC for the treatment of CF. It will also include an evaluation of the PK of TEZ and metabolites, and IVA and metabolites, following administration of VX-121 in TC with TEZ/IVA.

Parts A, B, and C (except Cohort A9) will be randomized, double-blind, and placebo-controlled to avoid bias in the collection and evaluation of safety and tolerability data during their conduct. Subjects will be randomized 3:1 to receive either active study drugs or placebo. Placebo has been chosen as the control treatment to assess whether any observed effects are treatment-related or simply related to the study conditions.

Predictive models suggest that the solubility of VX-121 may decrease in the presence of calcium-rich food such as milk and milk products, reducing the absorption and systemic exposure of VX-121. Therefore, in addition to randomized study drug administration described above, after a washout of at least 8 days all subjects in Cohort A3 will receive a single dose of open-label VX-121 suspension with milk to evaluate the effect of milk on VX-121 exposure.

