**Table 9-2 Parts A, B, and C: Study Restrictions**

Restricted Medication/Food/Activity a	Timing of Restriction	
	From (minimum)	To
Strenuous exercise (e.g., heavy lifting, weight training, and aerobics)	96 hours before first clinical laboratory testing	Completion of Safety Follow-up assessments

a See [Section 9.5.1](#) for guidance on concomitant medications.

b The restrictions on dairy consumption may be removed pending the results from Cohorts A3 and/or A9.

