#### **12.4.1 Pharmacokinetic Analysis**

The PK parameters of VX-121, TEZ and metabolites, and IVA and metabolites will be estimated using standard noncompartmental analysis methods. The analysis of PK results for all analytes will be based on the PK Set and will be described using descriptive statistics. Further details of the PK analyses will be provided in the CPAP.

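### Cohort A9's single fixed order leaves the tablet and milk effects inseparable from period, and any carryover would flatter the tablet and mask a milk reduction

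*Protocol*

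**What the plan says.** The Synopsis (Protocol Section 2, Study Design) describes A9 this way: "Cohort A9 has an open-label, single sequence design in which subjects will receive a single dose of VX-121 on 3 dosing occasions". Table 3-4, footnote h, fixes the order. It begins "Study drug will be administered as a suspension in the fed state on the Day 1 Visit", continues with the tablet in the fed state on Day 9, and ends "as a tablet in the fed state and with milk on the Day 17 Visit". About 8 subjects take all three treatments, at a planned 10 mg each, with at least 8 days between doses. There is no randomised order and no concurrent group.

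On carryover, Section 9.3.1 (Cohort A9) calls the interval adequate on the strength of preliminary clinical data, without giving a half-life. Table 3-4, footnote g, schedules a sample before each of the three doses and sampling to 168 h after each.

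On analysis, Section 12.4.1 says: "The analysis of PK results for all analytes will be based on the PK Set and will be described using descriptive statistics". It leaves further detail to the clinical pharmacology analysis plan (CPAP), as does SAP Section 4. The CPAP is not among the documents.

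On use of the results, Section 9.1.1 says the tablet "may be used instead of the suspension in any remaining cohorts of the study if supported by preliminary PK data from Cohort A9". Table 9-2, footnote b, adds: "The restrictions on dairy consumption may be removed pending the results from Cohorts A3 and/or A9".

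**The concern.** Treatment and period change together in every A9 subject. Whatever differs between Day 1, Day 9 and Day 17, apart from the product taken, enters the formulation or milk ratio in full. No analysis of these data can remove it, because no subject takes the treatments in another order.

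Carryover is a special case with a known sign. Drug left from the suspension adds to the tablet period, and drug left from both adds to the milk period. The first pushes the tablet/suspension ratio up. The second props up exposure with milk, when Section 9.3.1 expects milk to lower it. Both errors favour the decisions under consideration, namely adopting the tablet and relaxing the dairy rule.

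No section gives a reason for the fixed order. Supply does not obviously require it, since "Cohort A9 will not be initiated until all documentation required to support administration of the VX-121 tablet has been submitted to and approved", so both formulations should be usable from Day 1. The ratio may also matter after the switch: Section 9.6.2 describes Part D dosing in tablets, while Section 9.3.2 predicts Part D exposure from Parts A to C. If those earlier data come mainly from suspension, the A9 ratio is the link between them.

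**Working it through.** The documents state no power, precision or margin for A9, and Section 12.1 says that no formal sample size calculation was done. There is no plan figure to reproduce.

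**1. Can the effects be separated?** Take the log-scale model: subject + period + treatment.
- Parameters with 8 subjects: 8 + 2 (period) + 2 (treatment) = 12, on 8 × 3 = 24 observations.
- One sequence: the design matrix has rank 10. The two treatment contrasts coincide with the two period contrasts, so neither pair can be estimated apart from the other.
- The same 8 subjects spread over six balanced sequences: rank 12 of 12. A three-sequence Latin square split 3/3/2 also gives 12 of 12.

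**2. Size of a period effect.** Suppose the true ratio is 1 and log exposure shifts by 0.1 between periods 1 and 2. The expected tablet/suspension ratio is exp(0.1) = 1.105. The value 0.1 is illustrative; the documents show no period effect.

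For scale, assume a within-subject CV of 20%. Then s = √ln(1 + 0.20²) = 0.198. The paired 90% CI half-width with n = 8 is 1.895 × 0.198 × √(2/8) = 0.188, giving 0.83 to 1.21 around a ratio of 1. A shift of 0.1 is about half that half-width (0.1/0.188 = 0.53), and the interval would not reveal it.

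**3. Size of carryover.** The washout is 8 × 24 = 192 h. With one-compartment decline and no predose correction, the fraction of the earlier AUC still to come is r = 2^(−192/T½). With a true tablet/suspension ratio of 1:
- the tablet/suspension ratio reads 1 + r;
- a true milk/no-milk ratio m reads (m + r + r²)/(1 + r), which exceeds m whenever m < 1 + r.

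| Assumed T½ | r | Tablet/suspension, true 1 | Milk/no-milk, true 0.70 |
|---|---|---|---|
| 24 h | 0.4% | 1.00 | 0.70 |
| 48 h | 6.3% | 1.06 | 0.72 |
| 72 h | 15.7% | 1.16 | 0.76 |

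The 72 h milk entry, for example, is (0.700 + 0.157 + 0.025)/1.157 = 0.76, so a true 30% reduction reads as 24%. The 30% is an assumption. The half-lives are assumptions too, and the table shows how strongly the result depends on them.

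**4. Cost of estimating period.** Without period terms the model has 24 − 8 − 2 = 14 error degrees of freedom; with them it has 12. The one-sided 5% t quantile moves from 1.761 to 1.782. Using 8 rather than a multiple of 3 or 6 subjects changes the variance of a treatment contrast from 0.250σ² to about 0.254σ² for the 3/3/2 split. With six sequences, two of them used twice, it is 0.250σ² to 0.263σ², depending on which two are doubled.

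**The case against.** The best defence is that this is a secondary objective in about 8 healthy inpatients on standardised meals, with no equivalence claim. The tablet only *may* be adopted. Escalation in Parts B and C still reviews PK from the preceding cohort, and Parts A and B carry exposure caps. The protocol does justify the 8-day gap, and the predose samples on Days 9 and 17 allow carryover to be seen and subtracted. All of this stands and limits the severity. It leaves the period aliasing untouched, and neither document says how a non-zero predose value will be treated.

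Four stronger readings are tempting but not supported:

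- *Between-subject differences distort the A9 contrasts.* Every subject takes all three treatments and is his or her own control, so these differences cancel. They would only widen intervals under an unpaired analysis, which the documents do not propose.
- *No within-subject ratio is planned.* The protocol names only descriptive statistics, but it defers the detail to a CPAP that cannot be seen. The fair statement is that neither document commits to such a ratio. Section 12 requires the CPAP only before database lock, while the tablet decision may come earlier, on preliminary data.
- *The 8-day gap contradicts the 21-day gap.* Section 9.3.1 lets a subject join only one cohort "unless at least 21 days has elapsed before participation in another cohort), to avoid PK and/or PD carryover effects". That sentence explicitly excludes A9 and concerns re-enrolment across cohorts, where Part A doses are planned up to 90 mg. A9 has its own stated justification.
- *The A3 milk comparison sets 8 subjects against 6 different ones.* SAP Section 9.1 labels A3 results by sequence, which keeps the active-first subjects together. Pooling for the PK comparison is not shown.

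**Conclusion.** The concern holds for the fixed order. In A9 the formulation and milk contrasts cannot be separated from period; this follows from the design alone and needs no assumption. Its numerical consequence is conditional. A period shift of 0.1 on the log scale would produce an apparent ratio of 1.105 for equal formulations. Uncorrected carryover would be negligible at a 24 h half-life, about 6% at 48 h and about 16% at 72 h, always raising the tablet and masking a milk reduction. No half-life or period effect is documented, so it cannot be said that the A9 results will be materially biased. The change is worth making because two operational decisions may rest on these ratios and the repair is cheap.

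**What to change.** In Protocol Section 2, Section 9.1.1 (with Table 9-1), Section 9.3.1, Section 9.6.1 and Table 3-4, replace the single sequence with random allocation to orders in which all three treatments appear in all three periods. Either a 3-period Latin square or a six-sequence Williams design would serve in the same approximately 8 subjects, accepting slight imbalance. The Williams design is preferable if carryover is a worry, because it balances which treatment precedes which; a cyclic Latin square does not. Randomising only suspension against tablet and keeping milk last would not be enough, since milk would remain aliased with period 3.

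In Section 12.4.1 and the CPAP, commit to tablet/suspension and milk/no-milk ratios for AUC and Cmax with 90% CIs. Estimate them from a within-subject log-scale model with subject (or sequence), period and treatment, and state a rule for non-zero predose concentrations. Fix this before A9 data are used for the formulation decision, not merely before database lock. State the half-life that supports the 8-day interval.

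The cost is a randomisation list and revised wording, more than one treatment to prepare on each dosing day, and two error degrees of freedom. No extra subjects or visits are needed. If the sponsor has a reason to keep the order, the protocol should give it and acknowledge that both ratios then rest on assuming no period effect.
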